5.2.2 Exclusion Criteria

Subjects are to be excluded from the study if they meet any of the following criteria:

1. Discontinued study participation in Verastem-sponsored IPI-145-07
2. >3 months from confirmed PD on Study IPI-145-07
3. Richter's transformation or prolymphocytic leukemia
4. Autoimmune hemolytic anemia (AIHA) or idiopathic thrombocytopenia purpura (ITP) that is uncontrolled or requires >20 mg QD of prednisone (or equivalent) to maintain hemoglobin >8.0 g/dL or platelets >10,000 μ L without transfusion support
5. Known central nervous system (CNS) lymphoma or leukemia; subjects with symptoms of CNS disease must have a negative CT scan or negative diagnostic lumbar puncture prior to first dose
6. Use of any anticancer medication post documented PD on Study IPI-145-07 and prior to enrollment
 - Corticosteroids to manage CLL/SLL-related symptoms are allowed
7. Ongoing systemic bacterial, fungal, or viral infections at the time of initiation of study treatment (defined as requiring IV antimicrobial, antifungal or antiviral agents)
 - Subjects on antimicrobial, antifungal or antiviral prophylaxis are not specifically excluded if all other inclusion/exclusion criteria are met and there is no evidence of active infection at Screening and/or Cycle 1 Day 1 predose
8. Human immunodeficiency virus (HIV) infection
9. Prior, current or chronic hepatitis B or hepatitis C infection
10. History of alcohol abuse or chronic liver disease (other than metastatic disease to the liver)
11. Unable to receive prophylactic treatment for pneumocystis and herpes simplex virus (HSV)
12. Baseline QTcF >480 ms NOTE: this criterion does not apply to subjects with a right or left bundle branch block (BBB)
13. Concurrent active malignancy other than nonmelanoma skin cancer or carcinoma in situ of the cervix, bladder, or prostate not requiring treatment. Subjects with previous malignancies are eligible provided that they have been disease free for \geq 2 years
14. History of stroke, unstable angina, myocardial infarction, or ventricular arrhythmia requiring medication or mechanical control within the last 6 months

15. Unstable or severe uncontrolled medical condition (eg, unstable cardiac function, unstable pulmonary condition), or any important medical illness or abnormal laboratory finding that would, in the Investigator's judgment, increase the subject's risk while participating in this study

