Complete Response/Remission (CR): all of the criteria have been met, and subjects have no disease-related constitutional symptoms

Partial Response/Remission (PR): at least two of Group A criteria plus one Group B criteria have to be met. For subjects with lymphadenopathy at baseline as the only abnormal Group A

criteria (eg. no organomegaly, blood lymphocyte count $<4,000/\mu\text{L}$, and negative bone marrow), all Group A criteria plus one Group B criteria have to be met.

PR with Lymphocytosis (PRwL): For subjects with lymphadenopathy at baseline as the only abnormal **Group A** criteria (eg. no organomegaly, blood lymphocyte count $<4,000/\mu\text{L}$, and negative bone marrow) who have a $\geq 50\%$ reduction in lymphadenopathy plus one **Group B** criteria but with isolated progressive lymphocytosis (blood lymphocyte count $\geq 4,000/\mu\text{L}$).

Stable Disease (SD): absence of PD and failure to achieve at least a PR/PRwL

Progressive Disease (PD): appearance of any new lesions or at least one of the **Group A** or **Group B** criteria met with the following exceptions:

- Due to the pharmacologic property of duvelisib to mobilize CLL cells from tissues into the peripheral blood, isolated lymphocytosis should not be considered progressive disease in the setting of other indications of response such as reduced lymph node size or organomegaly or improvement in hemoglobin/platelets³
- If a new lesion or isolated increase in target lesion(s) may be attributed to another cause (eg, infection), these findings alone should not be considered to determine progressive disease, especially when observed in the setting of reduced lymph node size or organomegaly, or improvement in hemoglobin/platelets. Radiological persistence of these findings for >4 weeks is likely to indicate disease progression (CT scan confirmation required)

Table 9: SLL Response Criteria (modified from IWG)

Response	Lymph Nodes ^a	Spleen/ Liver	Blood Lymphocytes	Bone Marrow ^b
Complete Response (CR)	Regression to normal size	Normal size; nodules not present	<4000/ μ L	If infiltrate present at screening, infiltrate cleared on repeat biopsy

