Partial Response (PR) ^c	Decrease \geq 50% in SPD of up to 6 largest masses; no increase in size of other nodes	Decrease \geq 50% in SPD of nodules (or greatest transverse diameter for single lesion); no increase in size of liver or spleen	Decrease \geq 50% from baseline or <4,000/ μ L	Irrelevant if positive prior to therapy; cell type should be specified
Stable Disease (SD)	Failure to achieve CR/PR criteria or progressive disease			
Progressive Disease (PD) ^{d,e,f}	New lesions (>1.5 cm) or increase \geq 50% in the SPD from nadir of more than 1 node, or \geq 50% increase in the longest diameter of a node >1 cm in short axis	>50% increase from nadir in the SPD of any previous nodules; unequivocal increase in liver/spleen size or de novo appearance of nodules	Increase \geq 50% over baseline or nadir (whichever is lowest) and \geq 5,000/ μ L	

- Evaluated by CT (or MRI) with sum of the products (SPD) of multiple (up to 6) lymph nodes determined. Use of Positron Emission Tomography (PET) imaging is not indicated in CLL/SLL.
- Subjects with CR by CT (or MRI) assessment of lymph nodes, liver/spleen, and peripheral blood without a negative bone marrow result (at baseline or at time of response assessment) will be considered a PR.
- PRwL: subjects who have a \geq 50% reduction in lymphadenopathy, no organomegaly and a negative bone marrow (at baseline or at time of response assessment) with isolated progressive lymphocytosis (blood lymphocytes \geq 4,000/ μ L).
- PD must be confirmed by CT (or MRI) scan
- Due to the pharmacologic property of duvelisib to mobilize SLL cells from tissues into the peripheral blood, isolated progressive lymphocytosis in the setting of reduced lymph node size or organomegaly or improvement in hemoglobin/platelets should not be considered progressive disease in the setting of other indications of response such as reduced lymph node size or organomegaly or improvement in hemoglobin/platelets
- If a new lesion or isolated increase in target lesion(s) may be attributed to another cause (eg, infection), these findings alone should not be considered to determine progressive disease, especially when observed in the setting of reduced lymph node size or organomegaly, or improvement in hemoglobin/platelets. Radiological persistence of these findings for >4 weeks is likely to indicate disease progression (CT scan confirmation required)

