At each scheduled Disease Response Assessment, the Investigator will be asked to provide a clinical response based on the parameters provided in Table 8 and Table 9 and assessment of disease-related constitutional symptoms.

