8.2.2.5 New Cancers

The development of a new primary cancer should be regarded as an AE and will generally meet at least one of the serious criteria (see [Section 8.1](#)). New primary cancers are those that are not the primary reason for the administration of the trial treatment and have developed after the inclusion of the subject into the trial. They do not include metastases of the original cancer.

Progression of the disease under study (disease progression) is not an AE/SAE, unless fatal.

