4.2 Per-Protocol (PP) Analysis Set

The per-protocol (PP) analysis set includes all subjects in the AT analysis set who do not violate the terms of the protocol in a way that would significantly affect the study outcome, with treatment group designated according to actual study treatment received. Subjects who meet any of the following criteria may be excluded from this analysis set:

- Do not have documented diagnosis of CLL or SLL within medical records
- ECOG performance status >2
- History of Richter's transformation or prolymphocytic leukemia
- Prior exposure to a PI3K inhibitor (duvelisib arm) or a BTK inhibitor (both arms)
- Receive concomitant prohibited anticancer therapy
- Permanent discontinuation from study drug due to non-compliance

The PP analysis set will be a secondary analysis set for selected efficacy analyses.

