10 APPENDICES

A. PFS censoring rule

Censoring of PFS will be performed as detailed in the table below.

Primary PFS Censoring / Event Methodology

Situation	Date of Event or Censoring	Outcome
No adequate baseline disease status assessment	Date of first dose	Censored
No adequate post-baseline disease status assessment unless death occurs prior to first post-baseline assessment	Date of first dose + 1	Censored
No documented progression or death before data cutoff	Date of last adequate disease status assessment	Censored
Documented progression with ≤ 1 missing scheduled disease status assessment before progression	Date of the earliest assessment that results in a finding of unequivocal progression	Event
Death before progression being documented with ≤ 1 missing scheduled disease status assessment before death	Date of death	Event
Documented progression or death following a long gap between adequate disease status assessments (eg, 2 or more consecutive missed scheduled disease status assessments)	Date of last adequate disease status assessment before the gap	Censored
New anticancer treatment or procedure started before documented progression	Date of last adequate disease status assessment prior to new anticancer treatment	Censored

Note: Disease status assessment includes CT scans (chest, abdomen and pelvis), bone marrow aspirate and/or biopsy (may not be required of all subjects at all scheduled disease status assessments), CBC and differential count, focused physical examination, disease related constitutional symptoms for disease assessment, and ECOG performance status. An adequate disease status assessment is any disease status assessment for which the investigator review is able to arrive at a disease status (eg, CR, CRi, PR, PRwL, SD, and PD) per protocol-defined criteria.

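### A subject who transforms and starts new therapy before any Table 8/9 finding is censored in PFS and DOR rather than counted as a failure; the bias is upward, of unknown and probably small size

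*Protocol*

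**What the plan says.** **Transformation.** The documents mention it in two roles only. It is an entry exclusion (Protocol synopsis and 5.2.2, criterion 3): "Richter's transformation or prolymphocytic leukemia". It is also a possible reason for removal from the per-protocol set (SAP 4.2): "History of Richter's transformation or prolymphocytic leukemia".

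**Progression.** Under Protocol 6.3.6.2, a CLL subject progresses on "appearance of any new lesions or at least one of the" Group A or Group B criteria of Table 8. These cover nodes, liver, spleen, blood lymphocytes, platelets and hemoglobin. For SLL, Table 9 uses nodes, spleen/liver and blood lymphocytes, and a footnote adds that "PD must be confirmed by CT (or MRI) scan". The marrow cell for progression is empty in both tables, and neither has a histology item. At each scheduled assessment "the Investigator will be asked to provide a clinical response based on the parameters provided in Table 8 and Table 9", together with constitutional symptoms.

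**Events and censoring.** PFS and DOR end at progression or death (Protocol 3.2). When new anticancer treatment precedes documented progression, SAP Appendix A gives the outcome as censored at the "Date of last adequate disease status assessment prior to new anticancer treatment". An adequate assessment there is one that yields a status under the protocol's own criteria. SAP 7.2.2.1 and 7.2.2.2 apply this rule to both DOR and PFS. Protocol 6.3.6 ends disease assessments once other anticancer therapy begins.

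**The concern.** The plan treats transformed disease as a different state at entry, yet gives it no place among the failure events afterwards. A subject may transform, be diagnosed on a biopsy or marrow sample, and be moved to other therapy with no qualifying change in nodes, organs or blood counts. Clinically that subject has failed study treatment. In the analysis the subject leaves the risk set as though the censoring carried no information about prognosis. Kaplan-Meier estimation assumes that censored subjects have the same future risk as those who remain, and here that is plainly untrue.

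At stake are the PFS and DOR descriptions for duvelisib, the only arm that will be tabulated (SAP 7.2 and 8). Without a written rule, the handling of any such case would also be settled ad hoc on open-label data.

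**Working it through.** **1. Plan's own figure.** The plan gives no figure for PFS, DOR or transformation. Its one precision statement, ±12% around ORR at 75 per arm (Protocol 9.1, SAP 3.2), reproduces: the largest distance from estimate to exact binomial limit is 11.96 points. It does not bear on this point.

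**2. Path through the rules.**
- Pathology shows transformation. There is no histology criterion and the marrow progression cells are empty, so this alone does not give PD.
- New therapy starts. Protocol 4.3 lists the need for additional anticancer therapy as a stopping reason separate from progression.
- Appendix A censors at the last adequate assessment before that therapy.
- Assessments stop (Protocol 6.3.6), so a later Table 8/9 progression is not recorded.

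**3. Direction.** Take r subjects at risk just after the back-dated censoring time, and suppose *a* others fail before the transformation date, with no other censoring. Survival from the censoring time onward is then:
- just after the transformation, if it is counted: (r − a − 1)/r; if it is censored: (r − a − 1)/(r − 1). Censoring is higher by (r − a − 1)/[r(r − 1)].
- just before the transformation, inside the gap: (r − a)/r against (r − 1 − a)/(r − 1). Censoring is lower by a/[r(r − 1)].

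With r = 75 and an assumed a = 5, the gain after the transformation is 69/5550 = 0.0124 and the dip before it is 5/5550 = 0.0009. From the date of the uncounted failure onward, the curve can only be raised. The dip in the short stretch before it is negligible.

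**4. Size, illustration only.** Let f be the share of failures handled this way. With exponential times the counted hazard is (1 − f)λ, so the median is multiplied by 1/(1 − f): 1.02 at f = 2%, 1.05 at 5%, 1.11 at 10%. For scale, one case among 60 events is 1.7% and four among 40 is 10%. Both the counts and f are assumptions.

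A simulation used 75 subjects, 1000 runs and a 36-month cutoff. Transformations were censored back to the last Table 4 visit (Cycles 4, 8, 12, 18, 24, then every 6 cycles), and other failures were dated exactly. Kaplan-Meier medians in months, transformation counted → censored:

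| Assumed true median | f = 2% | f = 5% | f = 10% |
|---|---|---|---|
| 6 | 6.03 → 6.12 | 5.96 → 6.23 | 6.00 → 6.54 |
| 12 | 12.01 → 12.22 | 12.16 → 12.68 | 11.96 → 13.25 |
| 18 | 18.09 → 18.46 | 18.19 → 18.96 | 18.16 → 20.08 |

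At a true median of 12 months, 12-month PFS moves from 0.500 to 0.506 (f = 2%) and from 0.500 to 0.532 (f = 10%). At f = 0 nothing changes.

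The simulation takes all treated subjects. SAP 7.2.2.2 as worded restricts PFS to responders, which is a separate matter; with fewer events each case would weigh more.

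**The case against.** **The gap is narrow.** This largely stands. One new lesion, a 50% increase in a single node, organ enlargement, a lymphocyte rise or, in CLL, a disease-related fall in platelets or hemoglobin is enough for progression. Unscheduled assessments count (SAP 6.7). Early discontinuation brings a CT scan (Protocol 4.3, 6.3.6.1). Many transformations would therefore already be events, and a reader who infers that every transformation is censored goes further than the text.

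Some cases remain. For duvelisib the termination scan applies only before Cycle 12 Day 1, and it is waived after a response assessment within the previous 30 days. A biopsy-proven node that has grown by less than 50%, or transformation confined to marrow, need not meet any criterion.

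**The isolated-lymphocytosis exception.** A reader might infer that it would excuse a rise in prolymphocytes. The exception requires other signs of response, and its stated reason is the mobilization of CLL or SLL cells by duvelisib. The documents do not say that it covers transformed cells, so the point does not rest on it.

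**Unseen sources.** Protocol 9.4 ties the endpoints to the IWCLL/IWG criteria and the censoring to Study IPI-145-07. Neither source can be checked here. An investigator might record transformation as PD on the strength of the published criteria, and the event would then count. Appendix A, however, relies on protocol-defined criteria, which do not list it, so handling could differ between investigators.

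**Adverse events.** Protocol 8.2.2.5 says "Progression of the disease under study (disease progression) is not an AE/SAE, unless fatal", and a reader might infer that transformation is lost from safety as well. The two losses cannot coincide. If transformation is recorded as progression, it is a PFS event; if it is not, that exclusion does not apply and the general AE definition in 8.1.1 does.

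**Per-protocol set.** A reader might infer upward bias there too, because the SAP 4.2 criterion has no time limit. Such subjects only may be excluded, the item sits among entry-type criteria, and the set serves secondary analyses. The direction is not established either: dropping a responder who later transforms would lower the per-protocol ORR.

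**Conclusion.** The gap in definition and censoring is real, and every step of it is in the text. It applies only to pathologically confirmed transformation followed by new therapy before any Table 8/9 finding. For those subjects the censoring is informative and the bias in PFS and DOR is upward.

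The direction is supported; an amount is not. The documents give no transformation rate, expected PFS, event count or duvelisib sample size. The 2% to 11% lengthening of the median depends on the assumed 2% to 10% share of failures and on exponential times. It should not be read as an estimate: the true effect is probably small and may be nil. ORR in the all-treated set is unaffected, and no hypothesis test or comparison between arms depends on the result. This is a cheap improvement, not a flaw that undermines the study.

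**What to change.** Keep the change within the SAP.

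1. In Appendix A, above the new-anticancer-treatment row, add: pathologically confirmed transformation (Richter's or prolymphocytic leukemia); date of the diagnostic sample; event. Apply it to PFS and DOR.
2. Add a sensitivity analysis of PFS and DOR in which the start of new anticancer therapy before documented progression is an event. This also covers other treated failures with no Table 8/9 finding.
3. Optionally, word the SAP 4.2 criterion as transformation 'at baseline', so that on-study cases clearly stay in the per-protocol set.

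The cost is a few lines of text, one extra analysis, and retrieval of sample dates from pathology already obtained; no new procedure is needed. PFS and DOR may be slightly shorter. The row widens the event definition in Protocol 3.2 and may depart from the Study IPI-145-07 censoring promised in Protocol 9.4. It should therefore be recorded in SAP 8, and the sponsor should judge whether Protocol 9 calls for an amendment. It should be fixed before individual cases are reviewed.

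Progression also leads to withdrawal from treatment and from the study (Protocol 4.3, 4.4). Whether transformation should count as progression for those purposes is a clinical question, which the sponsor should reconcile with the entry criteria; no rule is proposed here.

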6.4 EARLY TERMINATION OF DUVELISIB OR OFATUMUMAB

Subjects on duvelisib who discontinue treatment prior to Cycle 12 Day 1 or ofatumumab subjects prior to Cycle 7 will have an ETT visit within 7 days of last dose of study drug or the decision leading to treatment discontinuation, which will include the following assessments.

If performed within previous 14 days, do not need to be repeated:

- Urine or serum pregnancy tests will be collected from all women of childbearing potential (WCBP)
- Concomitant Medications and Procedures collection
- AE and SAE assessment
- Blood chemistry
- Liver function tests

If performed within previous 30 days, do not need to be repeated:

- Disease Response Assessments:
 - Focused physical exam /constitutional symptoms
 - Bone marrow biopsy/aspirate (if indicated)
 - Hematology
 - ECOG
 - CT scan

6.5 POST-TREATMENT PERIOD

6.5.1 Safety Follow-up Visit (30 Days Post-Treatment)

6.5.1.1 Duvelisib

For subjects assigned to duvelisib, a visit should occur for 30+7 days after discontinuation of duvelisib administration as outlined in [Table 2](#). If possible, this visit should be conducted prior to initiation of any subsequent therapy. This visit may be a conducted as a phone screen as long as the study subject does not require laboratory and/or other assessments related to any new or ongoing AE, in which case a clinical visit will be required. Assessments should include:

- AEs/SAEs collection
- Concomitant medications and procedures collection

Following the last dose of duvelisib, subjects will continue assessments as described in [Table 2](#) and [Table 4](#).

6.5.1.2 Ofatumumab

For subjects assigned to ofatumumab, a visit should occur 30+7 days after discontinuation or last administration of ofatumumab. If possible, this visit should be conducted prior to initiation of any subsequent therapy. This visit may be a conducted as a phone screen as long as the study subject does not require laboratory and/or other assessments related to any new or ongoing AE, in which case a clinical visit will be required. Assessments include:

- AEs/SAEs collection

- Concomitant medications

Following the last dose of ofatumumab, subjects will continue follow-up as described in [Table 3](#) and [Table 4](#).

6.5.1.3 Follow-up

For subjects who completed treatment or discontinued treatment with duvelisib or ofatumumab early due to reasons other than disease progression and remain on study, CBC and differential count will be performed approximately 2 months after the last on-treatment Disease Response Assessment, and every 2 months thereafter through 18 cycles and every 3 cycles thereafter or until PD, subject withdrawal, or start of subsequent therapy. All other disease assessments should occur approximately 6 months after the last on-treatment Disease Response Assessment, and every 6 months thereafter until PD, subject withdrawal, or start of subsequent therapy. For subjects in the ofatumumab treatment arm, their final assessment will be at Cycle 24. The following assessments should be performed as outlined in [Table 4](#).

Every 2 months

- CBC and differential count

Every 3 months (from Cycle 18)

- CBC and differential count

Every 6 months

- CT scans of chest, abdomen and pelvis
- Bone marrow biopsy and bone marrow aspiration
- Focused physical examination, ECOG performance status, and disease-related constitutional symptoms

6.6 MISSED VISITS

If a subject misses a scheduled visit, the subject will continue on the protocol and attend the next scheduled visit. If a subject misses 2 scheduled visits, then the subject's continued participation in the study must be re-evaluated (see [Section 4.3](#) and [Section 4.4](#)).

